Time Frame: Measured at baseline (Month 0), post-intervention (month 9), and follow-up assessments at the end of years 2, 3, and 4.

3. **Motor Competence (MC).** All MC measures will be evaluated in an indoor space (i.e., gymnasium or designated indoor activity space) during the time allocated for movement and physical activity. As recommended to increase the predictive validity of MC for physical activity, we will assess MC using multiple measures of MC that include both process and product measures.⁶ All measures will be assessed concurrently.

Time Frame: Measured at baseline (Month 0), post-intervention (month 9), and follow-up assessments at the end of years 2, 3, and 4.

A. Process measure. The Test of Gross Motor Development (TGMD)⁵⁰ will be used to assess motor skill development and learning. The TGMD is a measure of fundamental motor skill competence in children ages 3 to 10 years and consists of locomotor (run, jump, gallop, slide, hop, leap, and skip) and object control skills (throw, catch, dribble, underhand throw, kick, one-handed forearm strike, roll, and two-handed strike off a tee). Scores for the two subscales (locomotor and object-control) of the TGMD will be reported as raw scores for each skill. Mean test-retest reliability coefficients were reported as .88 for locomotor items and .93 for object-control items.⁵⁰ Interrater reliability coefficients for both subscales were reported as .98.⁵⁰ The TGMD will be videotaped with digital video cameras by trained researchers. All TGMD videos will be coded by in the CMAH Lab under the direction of PI [name]. Specifically, PI [name] and

an approved research staff member will complete the video analyses. Inter-rater reliability will be established by another approved research staff member and Co-I [name], the developer of the TGMD will be available to consult if there are any issues on concerns. An overall score for total MC of 0 – 100 will be used for data analyses. (Previously approved in PROTOCOL HUM00108917, HUM0011789).

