- B. The **Perceived Fundamental Motor Skill Competence Scale (PFMSCS)** is a video-based assessment that allows the child to see the entire motor skill in action rather than a static picture.⁶¹ The scale is the identical layout and item structure to the PSPCSA but align with the 12 fundamental motor skills of the TGMD.^{50,64} Reliability for internal consistency ranged from .69 to .84, with a reliability of .84 for the combined subscale measure.⁶¹

For both assessments, children will (1) select the picture/video that is most like him or herself. One picture/video depicts a child who is competent and the other shows a child who is not skilled; (2) focus on the designated pictures/videos and indicate whether he or she is just a "little bit" or "a lot" like that child. Separate pictures/videos for girls and boys will be used in accordance with the manual procedures. The range of scores for each item on the subscale is 1 (low competence) to 4 (high competence). Both assessments are established tools within the preschool population and standardized test protocols will be used.^{60,61} Additionally, PI-[name] has a vast amount of experience with the implementation of the tool in preschool populations.¹⁰⁻¹¹ (Previously approved in PROTOCOL HUM00108917, HUM0011789). Also the Perceived Fundamental Motor Skill Competence Scale (PFMSCS is a digital video/media clip in order to be viewed review need to be presentation view of a powerpoint program).

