Aim 1: Examine the immediate post-intervention effect of CHAMP (compared to control participants) on MC, PMC, and PA in preschool-age children.

The immediate post-intervention effect of CHAMP (compared to control participants) on each outcome variable will be evaluated at post-intervention (month 9). We will examine descriptive statistics on both pre- and post-intervention measures of the outcome variables for each group. The change of MC, PMC, and PA (i.e., PA refers to time spent in MVPA) will be compared between two groups using regression models, adjusting for other confounding factors. Random effects will be included in the model to accommodate for the potential within-cluster correlation coming from the nature of how the data are collected. We will also investigate the amount of attrition from pre-intervention to post-intervention, and attempt to identify baseline (or pre-intervention) predictors of the likelihood of dropping out (as an indication of possible bias in the change estimates).

Aim 2: Assess the sustainable effect of CHAMP (compared to control) on MC, PMC, and PA across middle childhood.

We will use MMR to analyze the clustered longitudinal data from our RCT to assess the long-term effects of the CHAMP intervention on improving the three (3) outcome measures, MC, PMC, and PA. In this analysis, we can obtain the estimates of the long-term longitudinal intervention effect, by adjusting for confounding factors (i.e., sex). For PA, we will test for a possible delay before any significant change because of the difficulty of achieving health behavior change by adding time-lagged covariates related to behavior changes in the regression analysis. We will also conduct exploratory analyses to test interaction effects to understand potential modified intervention effects by different levels of behavior changes. The intervention is designed to promote a positive trajectory of children's MC, PMC, and PA, and we will specifically test interactions between intervention and time, and between baseline motor skill and time, to see which baseline measure is a stronger driver of increasing physical activity.

Aim 3: Examine and compare the immediate and long-term mediating effect of PMC on the relationship between MC and PA in preschool-age children in the CHAMP and control.

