Official Title: A PATH (Promoting Activity and Trajectories of Health) for Children

NCT Number: NCT03189862

Document Date: 8/17/2017

Statistical Analysis Plan

Analyses of primary outcomes

Before conducting outcome analysis, we will examine the range and frequency distributions for all variables and will transform variables when appropriate. Preliminary analyses will assess each outcome cross-sectionally at baseline and at all follow-up time points. We will compare study groups (ie, CHAMP vs Control) for comparability and change in variables over time. To study both the short-term (immediate) and long-term (sustainable) effects of CHAMP, we will assess all longitudinal outcomes by both summary statistics and descriptive data figures over the baseline, post-intervention and the start and end of the academic year during Years 2, 3 and 4. Since the samples will be collected in different classrooms and different preschools, our data will have a clustered structure, which means within-cluster correlations likely exist.

For such clustered longitudinal data, we will use primarily random effects in the following models to account for multilevel correlations among the measurements: Mixed Model Regression, Growth Curve Modelling and Structural Equation Modelling.⁹³⁻⁹⁶ Random effects are appealing here to account for some latent mediating factors that may exist in the study. We will use the Mixed Model Regression to determine the effects of our proposed intervention on primary and secondary outcomes (Aim 1 and 2). Growth Curve Models will be used to understand if, and how, time-course changes in motor performance, perceived physical competence and physical activity differ between the intervention and control groups and Structural Equation Modelling for mediation analysis (Aim 3).

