More specifically, in Aim 1, the immediate post-intervention effect of CHAMP (compared with control participants) on each outcome variable will be evaluated at post-intervention (Month 9). We will examine descriptive statistics on both pre-intervention and post-intervention measures of the outcome variables for each group. The change in motor performance, perceived physical competence and physical activity (ie, physical activity refers to time spent in MVPA) will be compared between two groups using regression models, adjusting for other confounding factors (eg, age and sex). Random effects will be included in the model to accommodate the potential within-cluster correlation coming from the nature of how the data are collected. We will investigate the amount of attrition from pre-intervention to post-intervention, and attempt to identify the baseline predictors of the likelihood of dropping out (as an indication of possible bias in the change estimates).

In Aim 2, we will use Mixed Model Regression to analyse the clustered longitudinal data from our RCT to assess the long-term effects of the CHAMP intervention on improving the three outcome measures: motor performance, perceived physical competence and physical activity. In this analysis, we can obtain the estimates of the long-term longitudinal intervention effect by adjusting for confounding factors that include sex and age. For physical activity and BMI, we will test for a possible delay before any significant change because of the difficulty of achieving health behaviour change by adding time-lagged covariates related to behaviour changes in the regression analysis. We will also conduct exploratory analyses to test interaction effects to understand potential modified intervention effects by different levels of behaviour changes. The intervention is designed to promote a positive trajectory of children's motor performance, perceived physical competence, and physical activity, and we will specifically test interactions between intervention and time and between baseline motor skills, perceived physical competence, and time to see which baseline measure is a stronger driver of increasing physical activity.

In Aim 3, we will apply the Growth Curve Models to understand if, and how, time-course changes in motor performance, perceived physical competence and physical activity differ between the intervention and control groups. This model is also used to determine a time

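### The Aim 2 question of which baseline measure drives physical activity more strongly has no direct comparison of the two slopes and no common scale

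*SAP*

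**What the plan says.** The SAP (Analyses of primary outcomes, Aim 2) fits a mixed model: "we will use Mixed Model Regression to analyse the clustered longitudinal data from our RCT to assess the long-term effects of the CHAMP intervention". It then adds: "we will specifically test interactions between intervention and time and between baseline motor skills, perceived physical competence, and time to see which baseline measure" has the greater influence on physical activity (PA). The sentence closes with its purpose: "perceived physical competence, and time to see which baseline measure is a stronger driver of increasing physical activity". No other sentence says how the two baseline measures are to be compared.

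The protocol (section E, Objective 1, Aim 2) puts the same question with a shorter list. Beside intervention by time, it names only the interaction "between baseline motor skill and time, to see which baseline measure is a stronger driver of increasing physical activity".

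The scales are set out in protocol section D:

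- **Motor competence (item 3).** For the TGMD, "An overall score for total MC of 0 – 100 will be used for data analyses". Product measures in other units (velocity, distance, catches) are also collected.
- **Perceived motor competence (item 4).** There are two instruments, a six-item pictorial subscale and a video scale aligned with 12 skills. Each item is scored from 1 to 4. Neither document says whether items are averaged or summed, or which instrument enters Aim 2.

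The SAP's only rescaling rule concerns distributions: "we will examine the range and frequency distributions for all variables and will transform variables when appropriate".

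**The concern.** The question is comparative, but the only procedure named is testing interaction terms. A test of whether a slope differs from zero says nothing about whether two slopes differ from each other. One significant term beside one non-significant term is compatible with equal effects. The sizes of the coefficients do not settle it either, because a slope per TGMD point and a slope per PMC point are in different units.

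The relative roles of MC and PMC in PA are central to the trial's rationale (protocol section C), so a statement that one is the stronger driver would be read with interest. As the plan stands, that statement could rest on chance or on units, and the rule for making it could be chosen after the data are seen. The protocol has a further textual problem: it asks which baseline measure is stronger but lists only one.

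**Working it through.** **Figure in the plan.** Neither document gives a sample size or power for this question. The nearest figure is the 212 children for the change in PA (protocol section E, sample size). It reproduces: 2 × (1.960 + 1.282)² × 27² / 12.1² = 104.6 per arm by the normal formula, and 105.6 with the t distribution, hence 106 per arm. Below, 212 serves only as a simulation size.

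**1. Does another section supply the comparison?**

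- The rescaling rule responds to the shape of a distribution and does not put two predictors on one scale.
- The Aim 3 growth curves compare arms over time, and the structural equation models address mediation by PMC. Neither contrasts two baseline-by-time slopes.
- If the SAP sentence means a three-way interaction (motor skills × perceived competence × time), that term shows whether one measure modifies the other. It does not rank them.

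**2. Tests against zero when the drivers are equal.** Let each test have power p (assumed; not in the documents) and let the tests be independent. P(exactly one significant) = 2p(1 − p).

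| p | Calculation | Result |
|---|---|---|
| 0.9 | 2 × 0.9 × 0.1 | 18% |
| 0.8 | 2 × 0.8 × 0.2 | 32% |
| 0.5 | 2 × 0.5 × 0.5 | 50% |
| 0.3 | 2 × 0.3 × 0.7 | 42% |
| 0.05 (both null) | 2 × 0.05 × 0.95 | 9.5% |

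At p = 0.5, correlation between the two estimates of +0.3 to −0.3 moves the 50% to between 40% and 60%.

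A simulation used 212 children, 4,000 runs per setting and equal standardised effects, with both measures in one model. At 46–49% power per test, exactly one term was significant in 50% of runs (baseline MC–PMC correlation 0) or 59% (correlation 0.3). Sharing a model therefore does not remove the problem. The simulation ignored clustering and repeated measures.

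**3. Raw slopes when the drivers are equal.** The ratio of the PMC slope to the MC slope is SD(MC) / SD(PMC). All SDs are assumed.

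- PMC as an item mean, SD(MC) 10 to 20 points and SD(PMC) 0.4 to 0.7: from 10/0.7 = 14 to 20/0.4 = 50, with 15/0.5 = 30 in the middle.
- PMC as a sum, using the middle values: six items give SD 6 × 0.5 = 3 and ratio 15/3 = 5; 12 items give SD 12 × 0.5 = 6 and ratio 15/6 = 2.5.

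The cases worked span 2.5 to 50. The lower end is not a bound: pairing SD(MC) 10 with a 12-item sum of SD 12 × 0.7 = 8.4 gives 1.2.

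**4. Direct contrast.** In the same simulations, a single test of the difference between the two standardised slopes declared a difference in 4.6–5.0% of runs when the slopes were equal.

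**The case against.** The strongest reply is that the plan leaves the comparison unspecified and does not commit to a wrong one. Much of this stands. The SAP does not say that the two terms will be tested in separate models, that p-values will be set side by side, or that raw slopes will be ranked. A reader might infer any of these, but the text does not support them. The percentages in step 2 are generic arithmetic with assumed power. The ratios in step 3 depend on assumed SDs and on a scoring choice that the documents leave open, so a 30-fold gap is not a property of this trial.

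The question is also secondary. Hypothesis 2 concerns CHAMP against control, and the preceding SAP sentence calls its own interaction tests exploratory, although it is unclear whether that label carries over.

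What the reply does not remove is that interaction tests are the one procedure named for a comparative question. Whether the terms share a model or not, the output is coefficients in unlike units, each tested against zero.

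A further fair point is that dividing by the SD does not make two scales fully comparable. The protocol reports test–retest reliability of .88 and .93 for the TGMD subscales, and internal consistency of .86 and .84 for the two PMC instruments. These differ in size and in kind. Equal true effects could still give unequal standardised slopes, and the roughly 5% error rate refers to equality of the observed standardised effects only.

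**Conclusion.** The concern holds for a secondary, interpretive question. The SAP asks which of two baseline measures is the stronger driver of PA, but the procedure it names cannot rank them, and no other section fills the gap. The protocol's matching sentence lists one baseline measure and so cannot compare MC with PMC; that part needs no assumption.

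The size can only be illustrated: 18% to 50% of trials with exactly one significant term at per-test power of 0.9 to 0.5, assuming equal drivers and independent tests, and raw-slope ratios of about 2.5 to 50 in the cases worked. It would be wrong to infer that this trial will misrank the drivers at a known rate, or that its primary comparison is at risk. The primary endpoint, the change in PA from baseline to immediate follow-up between arms, does not depend on this analysis.

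**What to change.** In the SAP's Aim 2 paragraph:

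1. Name one baseline score per construct, for example the TGMD total for MC and one named PMC scale with its scoring (mean or sum).
2. Fit one mixed model for PA with arm by time, baseline MC by time and baseline PMC by time, dividing each baseline score by its pooled baseline SD.
3. Estimate the difference between the two standardised slopes with a 95% CI. Call one driver stronger only if the interval excludes zero.
4. Label the result exploratory and non-randomised, since baseline MC and PMC are not assigned. Note that unequal reliability of the two scales limits the comparison.
5. Align protocol section E, Aim 2 with the SAP so that both name the same two measures.

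Baseline MVPA and its interaction with time need not be added. The SAP counts baseline among the outcome occasions, so if baseline PA stays in the outcome, that covariate would put it on both sides of the model.

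The cost is revised wording, a choice of scores before analysis and one contrast. No new data are needed. The downside is a little extra analysis work and a more cautious conclusion, because the interval may include zero and leave the drivers unranked.

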
for each child. In CHAMP, children are given opportunities to make choices on specific task engagement, participate in a variety of learning experiences and peer interactions (e.g., cooperative and independent), involve themselves in leadership roles, and are allowed to choose the length of practice time necessary to develop a specific aspect of a skill (i.e., based on personal capabilities).

The CHAMP session is designed to take place in a school gymnasium or large indoor open space (i.e., multipurpose room) that has been designated at each preschool center. The space needed will accommodate 25 – 28 preschool-children and two classroom teachers (i.e., 1 instructor and 1 assistant). For this study, the instructors will be graduate trained movement science specialists. Equipment for the implementation of CHAMP consists of items typically found in preschool movement or early childhood physical education programs or can be obtained for minimal costs (e.g., balls of various sizes, bean bags, cones of various height, striking objects, targets, etc).

Methodology

Research Design. The proposed study is a two arm cluster randomized control trial with follow-up. Classes of children will be randomly assigned to treatment (i.e., movement intervention – CHAMP or the normal movement program provide by their educational center (Control; outdoor free-play activity in a large playground area with a variety of play structures that promote movement and physical activity but no planned instruction nor activities).

Setting and Participants (Recruitment). This study will take place in three Head Start centers (i.e., Perry, Ford, and Beatty) located in Ypsilanti Michigan (Midwest). The racial make-up of the centers are 65.9% Black or African American, 19.14% White (non-Hispanic), 8.82% Hispanic/Latino, 3.26% Asian-Pacific Islander, 2.82 other races (two or more), and 0.06% Native American. Participants will be 300 preschool-age children age 3.5 years and older that encompass diverse settings (30 classes; 15 CHAMP Treatment and 15 Control; 150 preschoolers per condition). Thus, participants will primarily be from urban settings and include low and middle SES black/African American. The three Head Start centers are on the same campus for the three elementary schools (Grades K – 5) where the students will enroll for their formative schooling (i.e., Erickson, Adams Stem, and Holmes Elementary School), which will aid with retention over 3-years of follow-up.

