Growth Curve Models (GCM) will enable us to understand if, and how, time-course changes in MC, PMC, and PA differ between the intervention and control groups. This model is also used to determine a time window over which the intervention effect appears stronger. We will use Structural Equation Models (SEMs) to determine which hypothesized constructs may be responsible for intervention effect on longitudinal PA. Based on the results of our previous work, for example, we hypothesize that PMC will not mediate the relationship between MC and PA at baseline, but PMC will mediate the relationship between MC and PA immediately post intervention and across the 3-yr follow-up period. We will use Mplus software to fit SEMs, and the goodness of fit of SEM models will be assessed using multiple criteria such as Chi-square to degrees of freedom (df) ratio (<2) and the Root Mean Squared Error of Approximation (RMSEA <0.05).

Sample Size, Power Analysis and Sample Attrition. Sample size was calculated based on our primary endpoint, the change in PA between baseline and immediate follow-up. According to previous literature³², we anticipate a change score of 12.1 minutes of MVPA/day for the intervention group after 1 year, with a conservative estimate of the standard deviation (SD) as 27 MVPA/day. Such a change is accepted as a clinically meaningful change in improving PA among preschool children. To detect an adjusted 12.1 (SD=27) difference in PA after 1 year between intervention and control groups with 90% power at an alpha level of 0.05, we will need a total of 212 subjects (106 subjects per arm). To account for a total of a 30% loss to follow-up, we will recruit 298 subjects at baseline (149 subjects per arm). To maintain the statistical power as 90%, the needed sample size and the detectable differences in change of PA scores are summarized in Figure 6.⁶⁹ Cohort feasibility data supports no difficulties identifying subjects who meet initial inclusion criteria for this study (See Approach Section C.4.4.). With the proposed sample size, the relationship between the power we can achieve for analyzing the mean change of MC score and PMC score and their corresponding expected mean difference and SD appears in Figure 7.⁶⁹ Given expected larger effects on MC and PMC, power to detect differences across groups is larger for MC and PMC than that seen with PA.

[figure not shown]

Fig 6: Sample size to achieve 90% power for PA.

[figure not shown]

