window over which the intervention effect appears stronger. We will use Structural Equation Models to determine which hypothesised constructs might be responsible for the intervention effect on longitudinal physical activity. Based on the results of our previous work, for example, we hypothesise that perceived physical competence will not mediate the relationship between motor performance and physical activity at baseline, but perceived physical competence will mediate the relationship between motor performance and physical activity immediately post-intervention and across the 3-year follow-up period. We will use Mplus software to fit Structural Equation Models, and the goodness of fit of Structural Equation Models will be assessed using multiple criteria such as χ^2 to df ratio (<2) and the root mean square error of approximation (<0.05).

Our goal is to have limited missing data but there is a potential for missing data. Assuming that data are missing at random, multiple imputation techniques will be used to replace missing data.⁹⁷ Missing data will be assumed to be missing at random if no participant demographics or primary outcomes are correlated with missingness. Mixed-effects models allow for partial information to be included for individuals who may dropout before any post-intervention data collection periods. Missing values will be multiply imputed using available covariates by sequential imputation. This approach allows optimal use of the available data in analysis involving change measures.

Data management

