Overall Analysis Plans. We will apply transformations to assure normality, run descriptive statistics, and assess potential covariates to include. While maximum effort will be made to retain all participants and minimize the amount of missing data, we anticipate there will be some data lost-to-follow-up and incomplete measures. Therefore, we will address missing data in the analysis plan by applying advanced statistical techniques, such as “multiple imputations” using PROC MI in SAS and IVEWARE SAS macro. Our overall approach will be to employ multivariate analysis to assess associations among key variables using the appropriate models based on the distribution of the data (i.e., normal, categorical data, count data, reaction time data). Since this is a cluster-randomized trial, adjusting the covariates (e.g., child sex, age, race/ethnicity) will aid in controlling additional unbalancesess due to the limited sample size. All analysis will be done using SAS 9.3 or R 4.1.0⁹⁶⁻⁹⁸. Additionally, we will perform “intent to treat”

analysis and assume all subjects comply to the assigned group. Findings/results from the study will also follow the CONSORT guidelines.

Power considerations. When we calculate the sample size and power, we assumed the intra-cluster correlation is 0.3. The achievable power is calculated for a detectable effect size, which is the detectable mean difference standardized by the square root of sample variance. Given the randomization design with 70 children in the intervention group and 50 children in the control group, we have 80% power to detect a difference in cognitive SR, behavioral SR, or emotional SR with an effect size of 0.52 and a Type I error level of 0.05.

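### The SAP does not say that imputation carries the randomised class (or arm); if class is left out, the standard error of the CHAMP effect is understated when clustering and missingness are material

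*SAP*

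**What the plan says.** The protocol (Setting and Participants) randomises classes: "30 classes; 15 CHAMP Treatment and 15 Control; 150 preschoolers per condition", about 10 children per class. The SAP (Analyses of primary outcomes) accepts that "our data will have a clustered structure, which means within-cluster correlations likely exist". For Aim 1 it adds: "Random effects will be included in the model to accommodate the potential within-cluster correlation coming from the nature of how the data are collected". The supplement's two aims also get random effects for classroom.

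The missing-data paragraph of the same SAP section, repeated in the protocol's Missing Data paragraph, reads: "Missing values will be multiply imputed using available covariates by sequential imputation". It lists no imputation variables. It justifies imputation by its use for change measures, and change is what Aim 1 analyses. Just before, it says: "Mixed-effects models allow for partial information to be included for individuals who may dropout before any post-intervention data collection periods". It does not say which of the two approaches is primary.

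For the self-regulation supplement (SAP, Overall Analysis Plans), missing data are handled by techniques of which multiple imputation "using PROC MI in SAS and IVEWARE SAS macro" is given as an example. No cluster option is described. Where the SAP names adjustment variables, they are child characteristics: age and sex for the main trial, and sex, age and race/ethnicity for the supplement. Class appears only under random effects.

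**The concern.** An imputation model should carry at least the structure of the analysis model. Here the randomised unit is in the analysis model but is not specified for the imputation. Read literally, available covariates are child characteristics, so the text as written leads to imputation without class.

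A child imputed that way does not receive the class's shared deviation. The completed data then look less clustered than the real data, while the true sampling variance of the arm difference still contains the whole class effect. Rubin's rules add uncertainty for the missing values but do not restore the lost between-class variance. At stake are intervals that are too narrow and a type I error above nominal for Aims 1 and 2 and for the supplement. This does not depend on the missing-at-random assumption: it arises even when data are missing completely at random.

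**Working it through.** **Plan's own figure.** The protocol sizes the trial "To detect an adjusted 12.1 (SD=27) difference in PA after 1 year between intervention and control groups" with 90% power at alpha 0.05. The formula n = 2(1.960 + 1.282)² × 27² / 12.1² gives 104.6, so 105 per arm. The exact t version gives 106 (power 90.1%), which matches the stated 212. No ICC enters this calculation, so it offers none for MVPA.

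**Inputs.** K = 15 classes per arm, 10 children each, n = 150 per arm, SD 27 (variance 729). The ICC (ρ) is given only for self-regulation (0.3), so 0.01 to 0.30 is assumed for the main trial. The missing share f is 0.30 (protocol, Data Collection: over 3 years) or 0.165 (protocol, supplement, post-intervention). Assumptions: equal class sizes, missing completely at random, 20 imputations, arm in the imputation model, class not in it.

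**Step 1, ICC in the completed data.** Two classmates share a class effect only if both were observed, so the ICC becomes (1−f)²ρ. At f = 0.30 this is 0.49 × 0.30 = 0.147. Simulation gave 0.146. For ρ = 0.10 it is 0.049, and simulation gave 0.049.

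**Step 2, true variance of the arm difference.** 2 × 729 × [ρ/K + (1−ρ)/((1−f)n)]. At ρ = 0.30, f = 0.30: 1458 × (0.0200 + 0.00667) = 38.9, SE 6.24 min/day (simulated 6.31).

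**Step 3, variance reported.**
- Within-imputation: 1458 × (0.147/15 + 0.853/150) = 22.6.
- Between-imputation: 1458 × (0.30²/105 + 45/150²) = 4.17.
- Rubin total: 22.6 + 1.05 × 4.17 = 26.95, SE 5.19 (simulated 5.20).

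The ratio is 5.19/6.24 = 0.83, so the SE is 17% too small.

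**Other settings, same formulas, beside simulations under no effect (1,500 to 3,000 trials each where recorded).** The simulations differ in whether the imputation uses arm only or also a baseline measure, and in whether that baseline carries class effects.

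| Setting | Reported/true SE by formula | Ratio, simulated | Type I error, simulated |
|---|---|---|---|
| ICC 0.30, 30% missing | 5.19/6.24 = 0.83 | 0.79–0.88 | 8.5–11.2% |
| ICC 0.10, 30% missing | 4.29/4.71 = 0.91 | 0.86–0.91 | 6.9–8.2% |
| ICC 0.10, 16.5% missing | 4.22/4.49 = 0.94 | 0.93 | about 5–6% |
| ICC 0.05, 30% missing | 4.03/4.25 = 0.95 | 0.92–0.95 | about 5–6% |
| ICC 0.01, 30% missing | 3.81/3.84 = 0.99 | 1.01 | 4.3% |
| Supplement: 10 classes of 6 per arm, ICC 0.30, 16.5% missing | 0.92 | 0.89–0.93 | 6.4–6.7% |

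For the supplement, in SD units:
- True variance: 2(0.3/10 + 0.7/50.1) = 0.0879.
- Completed-data ICC: 0.835² × 0.30 = 0.209.
- Reported variance: 2(0.209/10 + 0.791/60) + 1.05 × 2(0.165²/50.1 + 9.9/60²) = 0.0751.
- Ratio: √(0.0751/0.0879) = 0.92.

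**Is the missing class term the cause?** With a random class intercept added to the imputation, the simulated main-trial ratios returned to 0.98–1.07 and type I error to 3.5–5.6%. A child-level covariate explaining 25% of within-class variance did not help (ratios 0.79 and 0.90 at ICC 0.30 and 0.10, 30% missing). Fixed class dummies overshot: at ICC 0.05 the SE was 18% too large, with type I error 1.3%.

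**The case against.** The strongest reply is that the defect is read out of silence. Neither document says class is left out, and class could count as an available covariate. That stands: a reader might infer that the SAP prescribes imputation with no class effect, but it only fails to specify one. Nor does the direction follow from the text, since entering class as fixed dummies would make the SE too large at low ICC. The gap still needs closing, because the open choice decides whether the SE is too small, about right or too large.

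Second, if the random-effects model is fitted to the observed outcomes, the problem does not arise, and the SAP leaves that open. This also stands. But the SAP ties imputation to change measures and never names the primary approach. The protocol's sensitivity analyses, planned as necessary over missing-data mechanisms, would not address clustering.

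Third, the largest figures combine inputs from different places. A reader might apply a 21% shortfall and 11% type I error to MVPA at month 9. The documents do not support that: the ICC of 0.3 is for self-regulation, the 30% loss is over 3 years, and Objective 1 has no month-9 loss figure. The accelerometer wear rule could add missing MVPA, but by an amount that is not stated.

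Fourth, sequential imputation can draw on earlier measurements that themselves carry class effects. With one covariate assumed to correlate 0.7 within and between classes, 30% missing gave a ratio of 0.91 and type I error of 6.6% at ICC 0.30, and 0.95 and 5.6% at ICC 0.10. The bias shrinks but remains.

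Finally, the supplement was simulated with the protocol's 60 per arm, whereas the SAP's power section has 70 and 50.

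**Conclusion.** The concern holds as a conditional one. Imputation is under-specified for a class-randomised trial, and carrying it out as described, without class, understates the SE of the CHAMP effect when clustering and missingness are material:

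- **ICC 0.30, 30% missing:** SE about 12–21% too small, type I error about 8–11%.
- **ICC 0.10, 30% missing:** about 9–14% and 7–8%.
- **Supplement, ICC 0.30 and 16.5% loss:** about 7–11% and 6.4–6.7%.
- **ICC 0.05 or below:** little or no type I error inflation.

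A reader might infer that the false-positive rate exceeds 5% throughout. It does not: at ICC 0.05 and 30% missing, one simulation gave 5.6%, against 5.7% for a class-level analysis of the observed data in the same trials. The main-trial size stays a range because the ICC for MVPA, MC and PMC and the month-9 loss are not given. The figures assume missingness completely at random, equal class sizes before loss and no preschool level, and a strong class-carrying covariate would lower them. This should be fixed, but it does not by itself invalidate the planned analysis.

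**What to change.** State in the SAP that the primary analysis is the likelihood-based mixed model with a random effect for the randomised class, fitted to all observed outcomes without imputing outcomes. Where imputation is kept (missing baseline values or covariates, sensitivity analyses), specify multilevel imputation with a random effect for the randomised class and with arm and baseline included. Say explicitly that fixed class dummies will not be used, and make the protocol's Missing Data paragraph agree.

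The cost is about two sentences, a different imputation routine and slightly wider intervals. The SAP already names R for the supplement; its main-trial section names only SAS 9.3, so the software statement there may need a matching line.
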